3.3.3 Women of Childbearing Potential

A woman of childbearing potential (WOCBP) is defined as any female who has experienced menarche and who has not undergone surgical sterilization (hysterectomy or bilateral oophorectomy) and is not postmenopausal. Menopause is defined as 12 months of amenorrhea in a woman over age 45 years in the absence of other biological or physiological causes. In addition, females under the age of 55 years must have a serum follicle stimulating hormone, (FSH) level > 40mIU/mL to confirm menopause.

*Females treated with hormone replacement therapy, (HRT) are likely to have artificially suppressed FSH levels and may require a washout period in order to obtain a physiologic FSH level. The duration of the washout period is a function of the type of HRT used. The duration of the washout period below are suggested guidelines and the investigators should use their judgement in checking serum FSH levels. If the serum FSH level is > 40 mIU/ml at any time during the washout period, the woman can be considered postmenopausal:

- 1 week minimum for vaginal hormonal products (rings, creams, gels)
- 4 week minimum for transdermal products
- 8 week minimum for oral products

Other parenteral products may require washout periods as long as 6 months.

3.4 Concomitant Treatments

3.4.1 Prohibited and/or Restricted Treatments

Restricted treatment for the different study periods are detailed below:

3.4.1.1 Restricted/Prohibited Treatments Prior to Enrollment/Randomization

- Oral corticosteroids > 10 mg/day within 14 days of dosing (Day 1), or corticosteroid therapy ≥ 1 mg/kg during the 4 weeks preceding enrollment
- Intravenous, intramuscular or intra-articular corticosteroids within 4 weeks of enrollment.

- Treatment started or an unstable dose of NSAIDs, pilocarpine, cevimeline (Evoxac®), topical corticosteroid eye preparations, lifitegrast (Xiidra®), cyclosporine eye drops (Restasis®) or autologous serum eye drops within 14 days of dosing (dose must be held for at least 12 hours prior to any study visit after Screening)
- Artificial tears and/or saliva are permitted, but must be held on the day of study visit
- Use of methotrexate, cyclophosphamide, cyclosporine, tacrolimus, azathioprine, MMF or leflunomide within 12 weeks of enrollment
- Treatment started or an unstable dose of hydroxychloroquine (Plaquenil®) within 8 weeks of enrollment. Doses higher than 400 mg/day are not permitted. Use of other antimalarials (chloroquine, quinacrine) is not permitted
- Use of rituximab within 6 months prior to enrollment or lack of recovery of CD19+ B cells > 10/μl at screening in any subject with prior rituximab use
- Previous treatment with other biologics either marketed or in development (eg, abatacept, tocilizumab, belimumab, TNF inhibitors) within 6 months prior to enrollment
- Live vaccine administration to subjects within 30 days of enrollment, during the screening or study periods, or for 8 weeks after completion of dosing

3.4.1.2 Restricted/Prohibited Treatments During Double-Blind Treatment Period

All restrictions during the double-blind period only apply to the management of symptoms for pSS.

For concomitant treatments for other conditions, see [Section 3.4.1.3](#). Some of the drugs used for other conditions may result in drug interactions and may be prohibited or restricted. Any medication initiated during the treatment period should be discussed with the BMS Medical Monitor.

Hydroxychloroquine (Plaquenil®)

All subjects who enter the screening period on hydroxychloroquine must remain on a stable dose of no more than 400 mg daily from the time of signing the informed consent for the duration of the study. New initiation of hydroxychloroquine, a daily dose > 400 mg/day, or a change in the dose of hydroxychloroquine is not permitted during the screening or dosing periods. The use of other antimalarials is not permitted.

Steroids

All subjects taking oral prednisone or its equivalent during screening must remain at a dose ≤ 10 mg/day for the entirety of the dosing period. Intra-articular, intramuscular (IM) or intravenous (IV) corticosteroid injections, or initiation of topical corticosteroid eye preparations are not permitted during the screening or dosing periods unless required for treatment of adverse events in consultation with the BMS Medical Monitor.

Ocular and Oral Lubricants

Subjects who enter the screening period on a stable dose of pilocarpine, cevimeline (Evoxac®), topical corticosteroid eye preparations, cyclosporine eye drops (Restasis®), lifitegrast (Xiidra®), or autologous serum eye drops are permitted to remain on these medications during the screening and dosing period, but must hold the dose(s) for at least 12 hours prior to any study visit until all study assessments are completed. These medications may not be initiated during the screening or dosing period. Artificial tears and saliva are permitted but must be held on the day of a study visit until all study assessments are completed.

Analgesics and NSAIDs

- NSAIDs doses should remain stable with the exception of decreases being permitted due to related adverse events, such as gastric toxicity.
- Analgesics
 - Acetaminophen (paracetamol) maximal dose 2 g/day
NOTE: combination products including acetaminophen and narcotic analgesics (eg, acetaminophen with codeine phosphate, acetaminophen with propoxyphene napsylate, acetaminophen with oxycodone HCl, acetaminophen with hydrocodone bitartrate, etc.) are allowed provided the acetaminophen component dosage is accounted for in the maximum of 2 g/day
 - Narcotic analgesics must not exceed 30 mg/day of morphine or its equivalent
 - Tramadol doses must be stable
 - Acetylsalicylic acid is allowed in low doses (eg, ≤ 100 mg/day) for cardiovascular prophylaxis

Immunosuppressives

The following medications are prohibited during the screening, dosing and follow-up periods:

- methotrexate
- cyclophosphamide
- leflunomide
- azathioprine
- cyclosporine
- tacrolimus
- MMF
- rituximab
- belimumab
- tocilizumab

- All investigational and approved biologic therapies (including but not limited to abatacept, etanercept, anakinra, infliximab, etc.)
- Use of any investigational drug other than study medication

Hormonal Contraceptives:

The use of hormonal contraceptives (oral, via implant/depot or via eluting IUD) are prohibited as a method of highly effective contraception due to safety concerns from transient liver function test elevations observed in the drug-drug interactions study (IM006032) with BMS-986142 and a combination oral contraceptive (ethinyl estradiol and the norethindrone acetate). In the study, a total of 10 of 16 subjects that were dosed with the oral contraceptive and BMS-986142 in combination had mild to moderate elevations of transaminases without an associated increase of total bilirubin. The majority of ALT elevations were < 3xULN. The maximum increase occurred in one subject with an ALT 5.8x ULN without accompanying total bilirubin elevation. Most subjects had no symptoms, however, 3 subjects had nausea, 2 subjects had vomiting and 1 had chills. All of the elevated transaminase levels returned to baseline. An evaluation of the cause of the transaminase elevation is ongoing, but no marked changes in the exposures of BMS-986142 or the components of the oral contraceptive were observed in a preliminary assessment of the data (i.e. no pharmacokinetic drug-drug interaction occurred during co-administration).

In addition, the use of oral or implantable estrogen-based hormone replacement therapy is also prohibited until additional drug interaction data becomes available. See Section 3.4.1.3.

[REDACTED]

3.4.2.2 Infections

Subjects who develop significant infectious complications during the study should be treated appropriately and have study medication withheld and restarted only when the infection is clinically resolved and the investigator considers it appropriate.

3.5 Discontinuation of Subjects Following Treatment with Study Drug

Subjects MUST discontinue investigational product (and non-investigational product at the discretion of the investigator) for any of the following reasons:

- Subject's request to stop study treatment or withdrawal of informed consent
- Any clinical adverse event (AE), laboratory abnormality or intercurrent illness which, in the opinion of the investigator, indicates that continued participation in the study is not in the best interest of the subject
- Termination of the study by Bristol-Myers Squibb (BMS)
- Loss of ability to freely provide consent through imprisonment or involuntarily incarceration for treatment of either a psychiatric or physical (eg, infectious disease) illness
- Unblinding a subject for any reason (emergency or non-emergency)
- Use of prohibited medication
- Development of new active manifestations of pSS requiring treatment with any non-protocol approved medications during the study
- Inability or subject's failure to comply with the protocol requirements
- Pregnancy
- Male subjects must discontinue treatment if their female partners become pregnant during the trial. After discontinuation, male subjects are required to continue using a highly effective method of contraception for a total of 35 days post-treatment completion
- Severe (eg, \geq Grade 3), drug-related AEs of infection, bleeding events/coagulopathy, or injection site reactions

- ANC < 500/mm³, confirmed by repeat
- Potential drug induced liver injury (see [Section 6.6](#) for definition)

In the case of pregnancy, the investigator must immediately notify the BMS Medical Monitor/designee of this event. In most cases, the study drug will be permanently discontinued in an appropriate manner (eg, dose tapering if necessary for subject safety). Please call the BMS Medical Monitor/designee within 24 hours of awareness of the pregnancy. If the investigator determines a possible favorable benefit/risk ratio that warrants continuation of study drug, a discussion between the investigator and the BMS Medical Monitor/designee must occur.

All subjects who discontinue study drug should comply with protocol specified follow-up procedures as outlined in [Section 5](#). The only exception to this requirement is when a subject withdraws consent for all study procedures including post-treatment study follow-up or loses the ability to consent freely (ie, is imprisoned or involuntarily incarcerated for the treatment of either a psychiatric or physical illness).

If study drug is discontinued prior to the subject's completion of the study, the reason for the discontinuation must be documented in the subject's medical records and entered on the appropriate case report form (CRF) page.

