6.4 Pregnancy

If, following initiation of the study drug, it is subsequently discovered that a study subject is pregnant or may have been pregnant at the time of study exposure, including during at least 5 half-lives after product administration (35 days for lulizumab), the investigator must immediately notify the BMS Medical Monitor (or designee) of this event and complete and forward a Pregnancy Surveillance Form to BMS Designee within 24 hours of awareness of the event and in accordance with SAE reporting procedures described in [Section 6.1.1](#).

In most cases, the study drug will be permanently discontinued in an appropriate manner (eg, dose tapering if necessary for subject safety). Please call the BMS Medical Monitor or designee within 24 hours of awareness of the pregnancy.

Protocol-required procedures for study discontinuation and follow-up must be performed on the subject.

Follow-up information regarding the course of the pregnancy, including perinatal and neonatal outcome and, where applicable, offspring information must be reported on the Pregnancy Surveillance Form.

Any pregnancy that occurs in a female partner of a male study participant should be reported to BMS. Information on this pregnancy will be collected on the Pregnancy Surveillance Form. In order for BMS to collect any pregnancy surveillance information from the female partner, the female partner must sign an informed consent form for disclosure of this information. Information on this pregnancy will be collected on the Pregnancy Surveillance Form.

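### Pregnancy is a mandatory stopping reason in Protocol 3.5, yet 3.5 and 6.4 stop study drug only in most cases, and 3.5 lets continuation be pursued without saying whether the Medical Monitor must agree

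*Protocol*

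**What the plan says.** Protocol 3.5 introduces its list of stopping reasons with "Subjects MUST discontinue investigational product (and non-investigational product at the discretion of the investigator) for any of the following reasons". The only discretion in that sentence concerns non-investigational product. Pregnancy is one of the listed reasons, as a single word with no exception and no cross-reference. The next bullet deals with partners: "Male subjects must discontinue treatment if their female partners become pregnant during the trial".

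A paragraph after the list deals with pregnancy again. It requires that "the investigator must immediately notify the BMS Medical Monitor/designee of this event" and asks for a call to the Monitor within 24 hours. It also says that drug is stopped in most cases, and it has a sentence on continuing: "If the investigator determines a possible favorable benefit/risk ratio that warrants continuation of study drug", then "a discussion between the investigator and the BMS Medical Monitor/designee must occur".

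Protocol 6.4 repeats the weaker stopping sentence: "In most cases, the study drug will be permanently discontinued in an appropriate manner". It has no sentence on continuing, and it ends the matter with an unconditional requirement: "Protocol-required procedures for study discontinuation and follow-up must be performed on the subject".

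**The concern.** Section 3.5 says in one place that a pregnant subject always stops and in another that she usually stops. An investigator with a positive test can find support there for either course. If continuation is considered, the text sets out how the question is raised but not how it is closed. The investigator makes a benefit/risk determination and a discussion follows, but the protocol does not say whether the Monitor's agreement is needed or what criteria apply.

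What is at stake is fetal exposure to a blinded investigational drug, and whether a subject who stays on drug would be within the protocol or in breach of its mandatory list.

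**Working it through.** There is no figure to reproduce. The check sets the provisions side by side and then asks how often the question could arise.

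1. **The list (3.5).** It has 13 bullets, and pregnancy is the 9th. The opening sentence makes each of them mandatory for investigational product.

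2. **The paragraph (3.5).** The drug is stopped in most cases, so by implication not in all. Pregnancy is the only one of the 13 reasons for which 3.5 itself goes on to contemplate continuing.

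3. **Section 6.4.** It has the weaker stopping sentence but not the continuation sentence, and then an unconditional requirement to carry out discontinuation procedures. It agrees fully with neither the list nor the paragraph in 3.5.

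4. **Neighbouring rules.** These point to a firm stop.
   - Section 3.3.1 excludes pregnant women at entry and requires contraception until 65 days after treatment.
   - The partner bullet in 3.5 is absolute, although Appendix 1 notes that partners do not receive study drug. The directly exposed subject therefore has the looser rule.
   - The pregnancy-test note in Table 5.1-2 asks for a confirmed negative test within 24 hours before dosing. Read as applying to every test in its row, it blocks dosing after a positive result. It could be read as Day 1 only, and it does not cover a pregnancy found between visits.

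5. **Does another section settle it?** Section 4.6 names pregnancy as a possible ground for breaking the blind, but tells the investigator to call for emergency unblinding only once discontinuation has been decided. Unblinding for any reason is itself on the mandatory list. A decision to continue could therefore only be made blind. That narrows the discretion without removing it. Nothing else in the supplied text reconciles the list with the paragraph.

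6. **How often it could arise.** Table 5.1-2 schedules pregnancy tests on Days 1, 29, 57, 85 and 127, which is 5 tests. Injections run weekly from Day 1, the last on Day 1 + 7 × 11 = Day 78, within an 84-day treatment period. A positive Day 1 test fails the entry criterion. Days 85 and 127 fall at or after the end of treatment. That leaves Days 29 and 57, or 2 of 5 tests, with dosing under way and still to come. A pregnancy found between those tests raises the same question. This count shows where the rule applies; it is not a measure of risk.

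**The case against.** The strongest defence is that this is a general rule followed by a specific one. The pregnancy paragraph comes straight after the list, so anyone who reads the bullet soon reaches the handling rule. The softer wording appears in two sections, which suggests that it is deliberate. On that view all that is missing is a pointer from the bullet and a statement that the Monitor must agree. This has some force: the documents do not prove that the sponsor meant an absolute stop. But it accepts that an edit is needed, and it does not explain why 6.4 requires discontinuation procedures without condition or why the partner rule is stricter.

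A reader might infer more than the documents support, in three ways.

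- **That nobody is named as deciding.** The investigator is named as making the benefit/risk determination, and both parties to the discussion are named. Only the final say is missing.
- **That a site could continue dosing on its own, or that two sites could act in opposite ways unseen.** Section 3.5 requires immediate notification and a call within 24 hours. Section 6.1 has pregnancy handled as a serious adverse event, and 6.1.1 requires a report to the sponsor within 24 hours. Continuation needs a further discussion with the sponsor's Monitor. Sponsor involvement cannot be avoided.
- **That the SAP confirms an absolute stop.** SAP 7.4.2 refers to 3.5 in one line for the reasons a subject must discontinue. It is a cross-reference and does not interpret the pregnancy paragraph.

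**Conclusion.** The contradiction is real and minor. Section 3.5 makes pregnancy a mandatory stopping reason and then treats stopping as usual rather than certain, 6.4 repeats the weaker wording, and the continuation route does not say whether the Monitor must agree.

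The consequences are limited. Few events are expected, on the assumption that the required contraception is used in a trial of about 75 subjects, or 120 at most. The supplied documents give no pregnancy rate, no number of women of childbearing potential and no fetal-risk figure, and the toxicity and risk/benefit sections are not in the supplied text, so no risk estimate is offered. Sample size, power, error rate and the primary analysis are unaffected.

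It still merits correction, because a stated rule leaves room for blinded investigational dosing in pregnancy against the protocol's own mandatory list, its entry criteria and its partner rule.

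**What to change.** Make three edits at the next amendment, one deletion and two replacements:

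- In 3.5, delete the sentence on continuing study drug after a benefit/risk determination.
- In the pregnancy paragraph of 3.5, replace the statement that drug is stopped in most cases with: *Study drug must be permanently discontinued.*
- Make the same replacement in 6.4.

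Keep the Monitor notification, the Pregnancy Surveillance Form and the follow-up requirements unchanged. The text then agrees with the mandatory list, the partner bullet and the pregnancy-test note in Table 5.1-2.

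The cost is a narrow investigator discretion, which the mandatory list already denies. If the sponsor does want an exception, the smaller edit is to add a cross-reference to the pregnancy bullet and require the Monitor's agreement. That would cure the inconsistency within 3.5, but it would leave the partner rule stricter than the rule for the exposed subject, and 6.4 would still need to be aligned.

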3.6 Post Study Drug Follow up

In this study, ESSDAI and ESSPRI as well as other efficacy measures at Week 12 are key endpoints of the study. Post study follow-up is of critical importance and is essential to preserving subject safety and the integrity of the study. Subjects who discontinue study drug must continue to be followed for collection of outcome and/or survival follow-up data as required and in line with Section 5 until death or the conclusion of the study subject's participation in the specified follow up period of the study, whichever comes first.

3.6.1 Withdrawal of Consent

Subjects who request to discontinue study drug will remain in the study and must continue to be followed for protocol specified follow-up procedures. The only exception to this is when a subject specifically withdraws consent for any further contact with him/her or persons previously authorized by subject to provide this information. Subjects should notify the investigator of the decision to withdraw consent from future follow-up **in writing**, whenever possible. The withdrawal of consent should be explained in detail in the medical records by the investigator, as to whether the withdrawal is from further treatment with study drug only or also from study procedures and/or post treatment study follow-up, and entered on the appropriate CRF page. In the event that vital status (whether the subject is alive or dead) is being measured, publicly available information should be used to determine vital status only as appropriately directed in accordance with local law.

3.6.2 Lost to Follow-Up

All reasonable efforts must be made to locate subjects to determine and report their ongoing status. This includes follow-up with persons authorized by the subject as noted above. Lost to

follow-up is defined by the inability to reach the subject after a minimum of three documented phone calls, faxes, or emails as well as lack of response by subject to one registered mail letter. All attempts should be documented in the subject's medical records. If it is determined that the subject has died, the site will use permissible local methods to obtain the date and cause of death.

If investigator's use of third-party representative to assist in the follow-up portion of the study has been included in the subject's informed consent, then the investigator may use a Sponsor-retained third-party representative to assist site staff with obtaining subject's contact information or other public vital status data necessary to complete the follow-up portion of the study. The site staff and representative will consult publicly available sources, such as public health registries and databases, in order to obtain updated contact information. If after all attempts, the subject remains lost to follow-up, then the last known alive date as determined by the investigator should be reported and documented in the subject's medical records.

4 STUDY DRUG

Study drug includes both Investigational [Medicinal] Product (IP/IMP) and Non-investigational [Medicinal] Product (Non-IP/Non-IMP) and can consist of the following:

- All products, active or placebo, being tested or used as a comparator in a clinical trial
- Study required premedication, and
- Other drugs administered as part of the study that are critical to claims of efficacy (eg, background therapy, rescue medications)
- Diagnostic agents: (such as glucose for glucose challenge) given as part of the protocol requirements must also be included in the dosing data collection

Table 4-1: Study Drugs for IM128035

Product Description / Class and Dosage Form	Potency	IP/ Non-IMP	Blinded or Open-Label	Packaging/ Appearance	Storage Conditions (per label)
BMS-931699-01 Injection ^a The composition of the drug product is 12.5 mg/mL, BMS-931699 (lulizumab) in 20 mM phosphate, pH 5.9, with 5% (w/v) sorbitol	12.5 mg/mL	IP	Open-Label	3 cc vial with 13mm opening, 1-panel / Open-label Appearance clear to slightly opalescent, colorless to pale yellow solution	Store refrigerated 2 – 8 °C Protect from light, Protect from freezing
BMS-986142-01 Film Coated Tablet	50 mg	IP	Blinded Label	Plain, yellow, round film coated tablet HDPE Bottle	Store refrigerated 2 – 8 °C Store in a tightly closed container
Placebo for BMS-986142-01 Film Coated Tablet, 50mg	Placebo	IP	Blinded Label	Plain, yellow, round film coated tablet HDPE Bottle	Store refrigerated 2 – 8 °C Store in a tightly closed container

Table 4-1: Study Drugs for IM128035

Product Description / Class and Dosage Form	Potency	IP/ Non-IMP	Blinded or Open-Label	Packaging/ Appearance	Storage Conditions (per label)
BMS-986142-01 Film Coated Tablet	150 mg	IP	Blinded Label	Plain, yellow, oval film coated tablet HDPE Bottle	Store refrigerated 2 – 8 °C Store in a tightly closed container
Placebo for BMS-986142-01 Film Coated Tablet, 150mg	Placebo	IP	Blinded Label	Plain, yellow, oval film coated tablet HDPE Bottle	Store refrigerated 2 – 8 °C Store in a tightly closed container

^a The clinical label will reflect the product name as “BMS-931699-01” to be linked with the product description on the vial

BMS will provide BMS-931699-01, BMS-986142-01 and matching placebo for BMS-986142-01 tablets to all investigating sites. For study drugs not provided by BMS and obtained commercially by the site, storage should be in accordance with the product label (eg, normal saline placebo for BMS-931699)

Pharmacy dosing manual will be provided separately to the sites.

